3.2 Study Outcome Measures

3.2.1 Primary Outcome Measures

The primary outcome measure is the Yale Brown Obsessive-Compulsive Scale (Y-BOCS) which assesses the impact, frequency and severity of both obsessive and compulsive symptoms in OCD. The Y-BOCS will be administrated at each time point during the 24-week study (baseline 1 session, baseline 2 if more than 7 days post baseline 1, W4, W8, W12, W16, W20 and W24).

3.2.2 Secondary Outcome Measures

The Structured Interview Guide for the Hamilton Depression rating scale, 17 item (SIGHD-17), Beck Anxiety Inventory (BAI), Sheehan Disability Scale (SDS), Dimensional Obsessive Compulsive Scale (DOCS), Clinical Global Impression scales (clinician and patient rated) will be used as secondary outcome measures at each time point (baseline, W4, W8, W12, W16, W20 and W24. The World Health Organisation Quality of Life (WHOQOL-Bref) will also be used as a secondary outcome measure which will be completed by participants at baseline, W12 and W20.

O-NAC Protocol

Version 7.0 12 DEC 2018

These measures will investigate the therapeutic effects of NAC for improving mood, anxiety, and quality of life. In addition, both the rater's and participants overall perspective of OCD severity and improvement with time will be assessed.

4 SUDY ENROLLMENT AND WITHDRAWAL

4.1 Subject Inclusion Criteria

Eligible participants must be:

- Between the ages of 18-75
- Have the desire and capacity to consent to the study and follow its procedures
- Have a primary diagnosis of OCD (NetSCID-5-CT, see section 6.1)
- Achieve a minimum of 16 on the Y-BOCS and no greater than 31 at time of entry into the study (a patient with Y-BOCS score higher than 31 will be referred for appropriate treatment).
- Taking psychotropic medication/s for their OCD, and continue to do so throughout the study period.
 - If using medication the dose must be stable, i.e. same dose of primary medication for minimum of 8-weeks (minimum 12-weeks if it is their very first medication trial).
 See Table. 5.2 regarding acceptable classes and doses of medications for the study

4.2 Subject Exclusion Criteria

Participants will be excluded from the study in the event of:

- Bipolar disorder*a
- Psychotic disorders*a
- Primary diagnosis of Obsessive-compulsive spectrum disorders including hoarding, body dysmorphic disorder, trichotillomania (secondary diagnosis permitted)
- Severe depression (as defined by HAM-D score of ≥24)
- Alcohol/substance abuse*
- Y-BOCS score of ≥32 (extreme OCD)
- Treatment refractory OCD (see Figure 4.1)

• Currently engaging in intensive psychological therapies for OCD (a 4-week washout will be required before reassessing eligibility), for example:

- o In-patient OCD programs
- Intensive out-patient programs, for example 15-17 CBT sessions (involving ERP) conducted by a clinician within a 4-8 week period as outlined by Franklin,
 Abramowitz, Kozak, Levitt, & Foa, 2000; Simpson et al., 2013; Simpson et al., 2008
- Online CBT courses, for example, 'This Way Up' or STOP by Swinburne University
- Medications with known or suspected negative interactions with NAC (see Table 4.2 for guidelines) as determined by the medical investigator/s

Table 4.2 Therapeutic agents that may interact with NAC

		Strength of	Evidence
Agent	Mechanism	interaction	level
Activated charcoal	Strongly binds to up to 96% of orally ingested	Moderate	Clinical
Activated charcoal	NAC (dose dependent)	Moderate	studies
Nitro-glycerine	NAC potentiates the activity of nitro-glycerine	Major	Clinical
Twitto grycerine	and causes hypotension	Wajoi	studies
Insulin (inhaled	NAC (inhalation preparations) may affect		Theoretical, -
preparations)	absorption of rapid acting insulin when taken	Moderate	based on
proparations)	concurrently.		pharmacology
Chloroquine	NAC may prevent the build-up of heme inside	Moderate	In vitro or
(Aralen)	cells and thus reduce Aralen's efficacy	Woderate	animal study
>200mcg selenium	Selenium is required for GSH production and	Moderate	In vitro or
2200mog colomani	thus, may confound NAC activity	Wodorato	animal study
Anti-coagulant/anti-	NAC may slow blood clotting (via nitric oxide		In vitro or
platelet medication	activity) and therefore, potentiate the effects	Moderate	animal study
platelet mealeation	of these medications		aa. stady
	NAC may lower blood pressure via GSH's		
Blood pressure	influence on nitric oxide activity. Further,	Moderate	In vitro or
medication	NAC may potentiate hypotensive effects of	ouorato	animal study
	ACE inhibitors		

O-NAC Protocol

(Table sourced from MIMS & Natural Medicine Database, https://naturalmedicines.therapeuticresearch.com/; viewed April, 2018)

- Allergy to NAC, sulfur or any component of the IP
- Serious and unstable medical conditions (eg. cancer)
- Recent gastrointestinal ulcers
- Pregnancy and lactation^b
- Participation in any other interventional study
- Cessation of primary medication for OCD

*Diagnosed by the NetSCID-5-CT. aClinician diagnosed or, if self-reported/suspected by participant, a letter from a clinician confirming exclusion of diagnosis will be required bFemale participants will be required to provide written consent at baseline that they will employ adequate contraception methods during the study period.

Figure 4.1 Treatment refractory OCD criteria

*Unsuccessful trial equates to minimum of 12 weeks of an SRI/clomipramine (where tolerated) within or above the specified dosage range (see Table 4.3) and ≤35% reduction in Y-BOCS score. In the event where a Y-BOCS score is not available to determine response, participants will be asked to describe their response to treatment as per CGI-I criteria (very much improved = 1, much improved = 2, minimally improved =3, no change = 4 etc.) as suggested by Pallanti & Quercioli (2006) to gauge stages of response to treatment in OCD (see table 4.4). A reported score of ≥3 will be deemed an unsuccessful trial.

Table 4.3 Classes and dosages of medications to be trialed (minimum 12-weeks with inadequate response) for defining patients with TR-OCD

Medication	Dosage range (per day)
Fluoxetine	60-80mg
Sertraline	>200mg
Paroxetine	>60mg
Fluvoxamine	300-350mg
Citalopram	60-80mg
Escitalopram	30-40mg
Clomipramine	200-300mg
Duloxetine	60-120mg
Venlafaxine	150-375mg
Desvenlafaxine	100-400mg

(Bloch, McGuire, Landeros-Weisenberger, Leckman, & Pittenger, 2010; Sansone & Sansone, 2011)

Table 4.4 Guidelines for stages of response to treatment in OCD

Stag	THE COLUMN	of.	90 C	no.	mco.
Stati	200	o_1	ICS	v	HSC

Stage of response	Stage	Description Not at all ill; less than 8 on	
Ι	Recovery		
		Y-BOCS	
II	Remission	Less than 16 on Y-BOCS	
III	Full response	35% or greater reduction of	
		YBOCS and CGI 1 or 2	
IV	Partial response	Greater than 25% but less	
		than 35% YBOCS reduction	
V	Non-response	Less than 25% YBOCS	
		reduction, CGI 4	
VI	Relapse	Symptoms return	
		(CGI 6 or 25% increase in	
		Y-BOCS from remission score)	
		after 3+ months of "adequate"	
		treatment	
VII	Refractory	No change or worsening with	
	•	all available therapies	

(Pallanti & Quercioli, 2006)

O-NAC Protocol

Version 7.0 12 DEC 2018

4.3 Treatment Assignment Procedures

4.3.1 Randomisation Procedures

Randomisation of participants to treatment groups (for the first 20-weeks of the study) will be determined by computerised random allocation. Recruited eligible participants will be assigned a participant number and provided capsules according to a corresponding IP number. Participant numbers are provided sequentially and the randomisation code is set up in a 2 by 2 block design, with no group identifying them (to avoid potentially unblinding researcher's if participants were randomised to medication bottles labelled A or B).

The last four weeks of the study will be a single blinded placebo run-out (see section 5.12). All participants will be given placebo capsules at Week-20 (researchers unblinded) and told that they may either be receiving placebo or active treatment for the final four weeks of the study. They will continue the same dose of IP from the preceding four weeks (see Table 5.1 for titration strategy).

4.3.2 Masking Procedures

Blinding will be achieved by enlisting a person outside of the project to code the treatments and maintain the key to this code until data collection is completed. The codes will only be broken in an emergency, such as a serious adverse event that requires knowledge of the treatment being taken in order to manage a participant's condition.

4.3.3 Reasons for Withdrawal

Participants will be withdrawn from the study in the following events:

- Y-BOCS ≥32
- Severe deterioration of OCD*
- Suicidal ideation ≥3 on the SIGHD-17
- If a score of ≥ 24 on SIGHD-17 emerges during the study, clinical advice from the medical monitors will be sought to determine if withdrawal or referral is warranted
- Substantial treatment changes**

- Cessation of IP for >7 consecutive days
- Pregnancy
- Occurrence of serious medical condition as determined by the medical monitors, including gastrointestinal ulcers
- Emergence of serious side effects/SAE (to be determined by medical monitors on a case by case basis)
- Commencement of medication with known contraindications with NAC (see Table 4.2) at the discretion of the medical investigator/s
- Participants wishing to withdrawal from the study or withdrawal due to the discretion of the Investigators due to participant safety or similar reasons.

*RAs will notify medical monitors when a participant's Y-BOCS score increase of >35% from baseline. The participant's subsequent participation will be determined by the medical monitors on a case by case basis as well as appropriate referral suggestions (if withdrawn) as required. **For example, entry into an in-patient CBT program, introduction of new psychological therapies, introduction of a new medication, or cessation of medication used for their OCD.

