4.3.4 Handling of Withdrawals

Participants will be asked to attend an exit visit in person to sign a withdrawal of consent form. Reasons for withdrawal will be detailed and recorded in the patients CRF by the RA. If participants are withdrawn from the study due to worsening of OCD symptoms (i.e. Y-BOCS \geq 32) or mood (medical monitor's decision in cases of \geq 24 SIGHD-17), referral back to their treating doctor for appropriate care will be advised. In cases of strong suicidal ideation/intent, the participant will be seen by one of the medical investigators of the study.

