5.10 Follow-up visits

Participants will be required to attend follow-up visits at Week-4, 8, 12, 16, 20 and 24. In these sessions, participants will be asked to provide an overview since their last visit, particularly any noticeable changes in their OCD, mental health, functioning and/or quality of life. Changes in treatment (pharmacological and/or psychological), drug and alcohol consumption, medical conditions and the occurrence of side effects, if any, will also be ascertained. The Y-BOCS symptom checklist will be re-administrated by the RA to identify current obsessive and compulsive symptoms, followed by Y-BOCS severity scale (including question 11 regarding insight) and SIGHD-17. At each follow-up visit, the participant will also be asked to complete the DOCS, BAI, SDS, PGI-S, PGI-I and SAFTEE. Upon conclusion of each follow-up visit, the participants blood pressure will be taken and the CGI-I and CGI-S completed by the RA. In addition, at Week-12 and Week-20, the WHOQOL-BREF will also be completed by the participant.

Participants will also be reimbursed for travel expenses totaling \$140-\$160 in the form of Coles/Myer gift cards (\$20 at each scheduled visit; \$160 in total if all study visits are completed and if the baseline sessions are completed on separate days, reflecting additional travel costs incurred to the participant).

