5.12 Placebo run-out

The final four weeks of the trial will be reserved for the assessment of potential withdrawal effects and to investigate any sustained response that may occur after ceasing the NAC/placebo. This will be carried out my means of an additional four week single-blinded placebo run-out. The researchers will be aware that all participants will be transitioning onto placebo from Week-20 for the following four weeks, however, the participants will not be aware and continue under the assumption they may be receiving placebo or active treatment as they consented to in the baseline session. To uphold ethical standards whilst maintaining blinding, the PICF will state that the dose of NAC/placebo may change throughout the study to allow for titration and assessment of benefit/effect at various doses.

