5.13 Withdrawal Visit

In the event of withdrawal, participants will be asked to detail their reasons for wishing to withdraw, or, if the decision of the researchers, the RA will record these reasons in the participants CRF. If willing, the participant will complete the Y-BOCS and SIGHD-17 with the RA and will complete the WHOQOL-BREF and SAFTEE. Finally, they will be asked to sign the withdrawal of consent form. If the participant specifies, all their data (including their stored genetic sample) can be destroyed and not included in the analysis. If not specified by the participant at the time of withdrawal, all their data will be used as outlined in the PICF.

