6.2.2 Yale Brown Obsessive-Compulsive Scale (Y-BOCS) – severity scale

The Y-BOCS (severity scale) was created in 1989 by Goodman and colleagues and is typically administrated as a 10-item instrument to provide a rating of severity regarding OCD symptoms. It is widely used in OCD clinical research and private practice and is well regarded as the gold standard for measuring the severity of both the obsessions and compulsions present in the disorder (Rapp, Bergman, Piacentini, & McGuire, 2016). Treatment sensitivity of the Y-BOCS has been demonstrated through its extensive use in clinical trials for OCD (Grabill et al., 2008). The Y-BOCS is a semi-structured, clinician administrated scale that asks the patients to reflect on the most prominent obsessive and compulsive symptoms separately over the past seven days, exploring frequency, impact/interference, distress caused and the person's effort to resist and ability to control the thoughts. A five point Likert scale ranging from 0-4 is used for each question, 0 equating to none or minimal impact/intensity and four of greatest severity. Scores are determined by the researcher based on the participant's self-reports as well as the researcher's own observations and interpretation during the session. The sum of the 10 items yields an overall score, which enables participant's OCD to be categorised as sub-clinical (0-7), mild (8-15), moderate (16-23), severe (24-31) and extreme (32-40). The Y-BOCS has demonstrated good criterion-related validity as patients diagnosed with OCD have received higher scores on the Y-BOCS compared to those with other anxiety disorders and healthy controls (Grabill et al., 2008). In addition, question 11 of the Y-BOCS will be administered at each visit which assesses the participant's insight into their obsessive and compulsive symptoms. A rating of excellent (=0), good (=1), mild (=2), poor (=3) and completely lacking insight (=4) can be determined on a Likert scale of 0 - 4, however, these scores are not included in the Y-BOCS total score.

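### Stopping IP for more than 7 days, a substantial treatment change or Y-BOCS ≥32 ends study participation, so scheduled Y-BOCS visits to Week 20 are not collected after exit

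*Protocol*

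**What the plan says.** Protocol section 4.3.3 opens its list with "Participants will be withdrawn from the study in the following events". The list includes "Cessation of IP for >7 consecutive days", "Substantial treatment changes" (for example in-patient CBT, a new therapy or drug, or stopping the OCD medication) and a Y-BOCS of 32 or more. These three are unconditional. Other entries, such as severe deterioration, SIGHD-17 ≥24 and serious side effects, go to the medical monitors case by case.

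Section 4.3.4 continues: "Participants will be asked to attend an exit visit in person to sign a withdrawal of consent form". Section 5.13 adds one efficacy assessment: "If willing, the participant will complete the Y-BOCS and SIGHD-17 with the RA". Data already collected are kept unless the participant asks for their destruction.

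Section 5.10 sets the schedule: "Participants will be required to attend follow-up visits at Week-4, 8, 12, 16, 20 and 24". No section says that these visits go on after withdrawal. The only contact described beyond the end of participation concerns unresolved adverse events (section 7.2.2).

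Section 8.1 applies intention-to-treat to all data, names MMRM on Y-BOCS as the primary efficacy analysis and adds an ANCOVA on change to a Week-20 LOCF endpoint.

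**The concern.** The rules treat stopping the product and leaving the study as one event. Two of the three triggers are post-randomisation events linked to treatment or care, and the third is a poor score on the primary outcome itself. The outcome therefore stops being measured because of non-adherence, added treatment or deterioration.

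For these participants the later Y-BOCS course must be supplied by assumption: MMRM borrows it from those who stay, and LOCF freezes the last value. Stopping for tolerability or for added treatment can also differ between arms. An SAP can choose how to treat the missing visits but cannot recover them, so only the protocol can settle this.

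**Working it through.** **Reading the sections together.** Section 4.3.3 ends study participation, section 4.3.4 adds a withdrawal-of-consent form, section 5.13 allows one optional Y-BOCS, and section 5.10 has no branch for participants off IP. The protocol does not state outright that later visits are dropped, but no other practical reading is left.

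**What partly fills the gap.**
- The Y-BOCS asks about the "most prominent obsessive and compulsive symptoms separately over the past seven days" (section 6.2.2). Under the >7-day rule an exit score, when given, describes a week wholly off IP. It does not describe the course to Week 20.
- For Y-BOCS ≥32 the triggering score is itself observed.
- The run-out is meant "to investigate any sustained response that may occur after ceasing the NAC/placebo" (section 5.12), but it is seen only in participants who reach Week 20.

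**Inputs for an illustration of IP cessation.** The 3-point effect is from section 8.1. The protocol gives no stopping rate, persistence of benefit, SD or correlation, so these are assumed:
- A proportion p of each arm stops, at random; last on-IP visits are spread evenly over W4, W8, W12 and W16.
- The effect builds linearly: 0.6, 1.2, 1.8, 2.4 and 3.0 points at W4 to W20.
- SD is 6 and the correlation rho is 0.5 between all visits.
- An exit score, if given, sits at the next scheduled visit.

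The choice of rho is consistent with the plan's own sample size. With f = 0.15, N = 200 and seven time points, λ = f²·N·m/(1+(m−1)·rho) = 0.0225×200×7/(1+6×0.5) = 7.875 on F(1,198). Power is 79.8%, and 202 participants are needed for 80%.

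**Closed form, no exit scores.** The mean level reached by a stopper is (0.6+1.2+1.8+2.4)/4 = 1.5 points. MMRM estimates 3.0, because it projects stoppers along the course of those who stay.
- All benefit lost: the all-randomised Week-20 effect is 3(1−p), which is 2.7, 2.4 and 2.1 at p = 10%, 20% and 30%. MMRM overstates it by 3p = 0.3, 0.6 and 0.9. LOCF gives 3(1−p)+1.5p and overstates it by 1.5p = 0.15, 0.30 and 0.45.
- Level reached is kept: the true effect is 3(1−p)+1.5p, which is 2.70 at 20%. The MMRM gap is 0.30 and the LOCF gap is zero.

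**With exit scores.** These values come from simulation with 400,000 per arm and a likelihood fit under missing at random. The MMRM Week-20 overstatement, in points, if all benefit is lost:

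| Stoppers giving an exit score | p = 10% | p = 20% | p = 30% |
|---|---|---|---|
| none | 0.30 | 0.61 | 0.89 |
| half | 0.25 | 0.48 | 0.70 |
| all | 0.19 | 0.37 | 0.51 |

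At 20% with half giving exit scores, the gap is 0.48 if all benefit is lost, about 0.38 if half is kept and 0.27 if the level reached is kept. With no true effect and equal stopping it is zero. The LOCF gap with all benefit lost is 0.15 at 20% with half giving exit scores, and about zero with all. That last result depends on the assumed flat course after stopping.

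**Effect of continued visits** (all benefit lost, half of the remaining stoppers giving an exit score). The MMRM gap falls from 0.25 / 0.48 / 0.70 to 0.12 / 0.22 / 0.30 if half of stoppers continue visits, and to 0.06 / 0.11 / 0.14 if three quarters do.

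**The case against.** A reader might infer that section 4.3.3 contradicts section 8.1. It does not. Analysing everyone as randomised with whatever was collected fits the wording of section 8.1, and section 5.13 keeps the data of those who leave. The protocol never names a treatment-policy effect at Week 20; that yardstick is the reviewer's choice.

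Next, this is an augmentation trial on stable background care (sections 4.1 and 5.5). A Y-BOCS taken after in-patient CBT or a new drug answers a different question, and an estimate as if background care had stayed stable is a defensible target. This stands for treatment change and is why such visits need flagging. It has much less force for the >7-day rule, where the participant has simply stopped the product.

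The calculation also models one trigger of three. Loss of benefit fits IP cessation. It does not fit added therapy, which may lower Y-BOCS in both arms, or Y-BOCS ≥32, where exit follows the outcome. Complete loss is the adverse end of the range. The gap is also below one standard error: unadjusted, with 100 per arm and SD 6, 6×√(2/100) = 0.85 points. With equal stopping it inflates a real effect but creates no false positive. All of this stands and limits the size of the point. It does not supply the missing visits.

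**Conclusion.** The point holds as a design weakness worth fixing, not as an internal contradiction. After any of the three triggers the scheduled Y-BOCS visits to Week 20 are not collected. The effect in all randomised participants then depends on missing at random or on LOCF, with at most one optional exit score per stopper as a check.

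For IP cessation, with 20% stopping per arm and half giving exit scores, the MMRM overstatement at Week 20 runs from about 0.3 points (level reached kept) to about 0.5 (all benefit lost). The true effects are then 2.7 and 2.4 points. These figures rest on assumed rates, persistence, SD and correlation. The bias from the other two triggers, and from stopping that differs by arm, is not quantified; with unequal stopping it could go either way.

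A reader might also infer that collecting these visits lowers power from the planned 0.80. That comparison is not valid, because 0.80 is not the current plan's power once stoppers' visits are missing.

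**What to change.** - Keep the clinical rules in section 4.3.3, but word them as reasons to stop IP.
- Invite participants who stop IP, for more than 7 days or under another rule, to continue the already scheduled Y-BOCS visits to Week 20 when clinically appropriate. Referral to the treating doctor is compatible with this.
- Use the withdrawal-of-consent form only when a participant refuses further participation.
- Record the date of and reason for stopping IP separately from leaving the study.
- Include the later data in the intention-to-treat analysis. Flag visits after a substantial treatment change so that an analysis without them can also be given; the rules force IP to stop at that point, so those scores mix imposed discontinuation with new treatment.

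The cost is a protocol and PICF amendment, attendance at visits already in the schedule, and a possibly smaller estimated effect. The change does not reach participants who refuse further visits. The case for it is less reliance on untestable assumptions, not more power.
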